5.7. Analysis of Effect of Reported Emollient Use

Because the intervention uses an accessible, non-prescription topical emollient, either study arm might have users and non-users (compliant/non-compliant with study assignment). In the spirit of a *per-protocol analysis*, similar to the main analysis, we will classify participants by their reported emollient use (>weekly, on average, for the time up to diagnosis or end of follow-up) rather than assigned intervention arm. Under this coding, some participants assigned to the treatment arm might be non-users, and others assigned to the control arm may report regular emollient use; those individuals would be in different groups than under the main analysis, which uses assigned treatment arm.

Parent-reported frequency of emollient use (in days per week) will be summarized for the intervention and control arms for each quarterly follow-up time point from age 3 to 24 months (8 quarters). In this analysis, we will exclude observations after a diagnosis of AD, because emollient use is likely to reflect treatment rather than prevention. For example, if a parent reports a diagnosis of AD on the 9-month contact, that child's emollient use at 3 and 6 months will be included, but not 9 months or later. All of the definitions of AD diagnosis will be considered, i.e. GS-AD, PR-AD, CEQ-AD, etc. For missing responses, we will carry the last observation forward. Distributions over time will be graphed.

The relationship between frequency of emollient use and AD will be tested using a variable that is the average of each individual's frequency responses. We hypothesize that the intervention will increase the frequency of emollient use, and that more frequent emollient use will be associated with lower incidence of AD. If this is true, we expect that frequency will be associated with study arm (using a two-sample t-test or Wilcoxon rank-sum test, if skewed), that study arm will be associated with prevalence of AD (primary analysis), that higher frequency of emollient use will be associated with lower prevalence of AD (Equation 1 with emollient frequency substituted for study arm), and that including both treatment arm and emollient frequency in a model with AD as the outcome will change the estimate of treatment effect, which will be taken as evidence that frequency of emollient use is in the causal pathway.

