1.5 Potential Risks and Benefits

1.5.1 Potential Risks

The emollients used in our current proposed study will be used in a similar fashion to how they are being used currently by the general public with only slight changes that should not change the safety profile of the emollients. Data from two published studies and our unpublished data reveal over 70% of parents are already using moisturizers on a daily basis on their infants.^{34,35} These data reveal parents primarily use watery lotions. Our hypothesis is that a basic moisturizer with higher lipid content than a typical lotion will reduce the risk of developing atopic dermatitis by providing better barrier repair than water-based lotions. We also hypothesize that more frequent use of a thicker emollient (i.e. daily) will lead to enhanced protection of the skin barrier than current skin care practices and thus reduce the probability of developing AD.

The daily use of moisturizers in infants in our proposed study will likely not pose an increased risk beyond current standard usage. The main risk of the emollient would either be the development of an irritant contact dermatitis or rarely an allergic contact dermatitis to an emollient component. Theoretically, occlusive moisturizers could increase the risk of a skin infection, however this has not been seen in previous clinical studies of emollients in neonates. Moisturizer marketing campaigns currently promote the daily use of moisturizers in infants. Parents will have a choice of multiple legally marketed moisturizers for this study that are all freely available over-the-counter.

Parents in the intervention arm will select an emollient from the approved moisturizers list to use on their baby over the course of the study. These emollients do not pose any additional known risk to newborns or infants beyond current usage patterns in the community.

There is a risk of loss of confidentiality. The study team will take precautions to protect the confidentiality of participant information.

1.5.2 *Potential Benefits*

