3.4. Adherence

Participants in the intervention arm receive instructions to apply emollient daily, while those in the control arm are asked to refrain from emollient use. Frequency of emollient use, measured in days per week, is assessed for participants in both arms at each of the quarterly contacts from when the child is 3 months old to 24 months old. Participants are reminded of instructions per treatment arm at each quarterly and annual contact. Frequency of emollient use will be analysed as described in section 5 below.

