3.6. Analysis Populations

The **Intention-to-Treat (ITT) Population** will contain all randomized participants. Missing outcomes will be multiply imputed to reduce bias without exaggerating precision per recommendations by Little and Yau for longitudinal studies³.

The **Complete Case Population** will include the subset of participants with non-missing primary outcomes.

The **Per-Protocol Population** will assign participants who report emollient use to the intervention arm (regardless of randomization), and those who report no emollient use to the control arm. This dataset will be used to estimate the relationship between frequency of emollient use and AD.

The **Safety Population** includes all randomized participants. Safety outcomes are reviewed regularly by the DSMB.

The **AD Population** includes children with diagnosed AD (chart review).

4. Trial Population

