			Baths/week	Count (0-7+)	p%(x/n) n, mean, SD, Median, min, max
			Prior emollient use	Binary(Y/N)	p%(x/n)
			Prior emollient type	Categorical	p%(x/n)
			Prior emollient brand	Descriptive	p%(x/n)
Emollient Choices	Treatment Group	Baseline 24m or last refill	Prior emollient use per week	Count (0-7+)	p%(x/n) n, mean, SD, Median, min, max
			Gender	Binary(M/F)	p%(x/n)
			Ethnicity	Binary(Hispanic)	p%(x/n)
			Race	Categorical	p%(x/n)
			Education level	Categorical	p%(x/n)
			Emollient choice-baseline	Categorical	p%(x/n)
			Emollient choice-end of study	Categorical	p%(x/n)
			Switched from baseline	Binary(Y/N)	p%(x/n)

Table Title	Population	Time Point(s)	Endpoint	Endpoint Type	Summary Statistics by Treatment Assignment
Cumulative incidence of AD	ITT	24m	Primary outcome: Provider diagnosis of AD in patient chart	Binary(Y/N)	Relative risk(RR) for cumulative incidence
	ITT	12m,24m	Provider diagnosis of AD in patient chart at age 1 year and age 2 years	Binary(Y/N)	RR
	Complete case	12m,24m	Provider diagnosis of AD in patient chart (complete case)	Binary(Y/N)	RR
	ITT	12m,24m	Cumulative incidence of AD by parental report of provider diagnosis	Binary(Y/N)	RR
	ITT	12m,24m	Cumulative incidence of AD by parental report of Children's Eczema Questionnaire	Binary(Y/N)	RR
Age of onset of AD	ITT	All time points	Age of onset by chart review, parent report	Time to event	Kaplan-Meier
Skin Problems	ITT	12m,24m	Dry Skin	Binary(Y/N)	p%(x/n)
			Diagnosed eczema	Binary(Y/N)	p%(x/n)
			Red rash	Binary(Y/N)	p%(x/n)
			Itching	Binary(Y/N)	p%(x/n)
			Areas of rash	Categorical	p%(x/n)
Skin infections	ITT	12m,24m	Presence/absence at any time	Binary(Y/N)	p%(x/n)
			Type	Categorical	p%(x/n)
Rash treatment	AD population	12m,24m	Rash treatment Y/N	Binary(Y/N)	p%(x/n)
			Prescription treatment Y/N	Binary(Y/N)	p%(x/n)
			OTC treatment Y/N	Binary(Y/N)	p%(x/n)
			Specific type	Categorical	p%(x/n)
Skin care	ITT	12m,24m	Baths/week	Count(0-7)	p%(x/n) n, mean, SD, Median, min, max
			>2 baths/week	Binary(Y/N)	p%(x/n)
		12m,24m	>1 bath/week	Binary(Y/N)	p%(x/n)
		All time points before AD diagnosis, if applicable	Frequent emollient user: Report 3 or more days per week at majority of follow-up points	Binary(Y/N)	p%(x/n)
		Q3 months	Moisturizer use Y/N	Binary(Y/N)	p%(x/n)
			Emollient use days/week	Count(0-7)	n, mean, SD, Median, min, max
			Emollient type	Categorical	p%(x/n)
			Which emollients	Categorical	p%(x/n)

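### The SAP 5.7 exposure models count days per week of emollient use without regard to product, so lotion reported as emollient would dilute the frequency–AD association and the causal-pathway reading

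*SAP*

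**What the plan says.** SAP 3.4 fixes the adherence measure: "Frequency of emollient use, measured in days per week, is assessed for participants in both arms". SAP 3.6 builds the per-protocol population from reported use alone: anyone reporting emollient use counts as intervention, whatever their randomisation. SAP 5.7 has three parts that rely on exposure:

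- **Classification.** In place of assigned arm, "we will classify participants by their reported emollient use", with the line drawn at more than weekly on average, up to diagnosis or end of follow-up.
- **Association.** The link between frequency and AD "will be tested using a variable that is the average of each individual's frequency responses".
- **Causal pathway.** Arm and frequency enter one model, and a shift in the arm estimate is to be read as evidence that frequency lies on the causal path.

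Protocol 10.4.3 uses three or more days per week. None of these definitions names a product.

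Protocol 1.5.1 treats product as part of the treatment: "Our hypothesis is that a basic moisturizer with higher lipid content than a typical lotion will reduce the risk of developing atopic dermatitis". It puts daily moisturiser use among parents at over 70% and adds: "These data reveal parents primarily use watery lotions". Its frequency hypothesis concerns a thicker emollient.

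SAP Table 4 lists "emollient type" and a row for which emollients were used, both as categorical summaries by treatment assignment in the ITT population. The only planned model that uses product is the exploratory ceramide comparison (SAP 5.2, item 4). It separates products within the treatment arm and keeps all controls as one reference group.

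**The concern.** The treatment is a kind of product used at a given frequency, but the exposure variables record only the frequency. A control infant whose parent reports daily lotion as emollient use would sit in the same exposure group as an intervention infant given the study product daily. An intervention family that went back to lotion would still look adherent.

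Two readings are at stake. The frequency–AD association would be pulled towards no effect if lotion protects less than the study product, as the protocol hypothesises. The causal-pathway model could also show an arm effect that frequency does not explain, even where the whole effect ran through the lipid-rich product. The ceramide comparison cannot repair either, because it ignores what controls used.

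**Working it through.** **Inputs from the documents.** Control risk 24%, intervention risk 16.8%, RR 0.70, two-sided alpha 0.05, 80% power (SAP 2.3, 3.1). Allocation 1:1 (SAP 2.2). Feasibility-trial adherence 85.2%, defined as use at least five times a week at 6 months (protocol 1.3). Background daily moisturiser use over 70% (protocol 1.5.1).

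**The plan's own figure.** n per arm = [1.960·√(2·0.204·0.796) + 0.842·√(0.24·0.76 + 0.168·0.832)]² / 0.072² = (1.117 + 0.478)² / 0.005184 ≈ 491. This matches SAP 2.3 and is not in dispute; it only anchors the risks used below.

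**Assumptions for the illustration.** A share a = 0.85 of the intervention arm uses the product regularly and the rest use nothing. A share c of controls uses lotion regularly and the rest use nothing. Non-users have 24% risk, the product RR is 0.70, the lotion RR is L, and there is no confounding. With equal arms the base risk cancels:

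RR(user vs non-user) = (a × 0.70 + c × L) / (a + c)

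The power columns assume 500 analysed per arm (625 × 0.80) and a two-sided 0.05 test of two proportions with the resulting unequal groups.

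| c | RR, L = 1.0 | RR, L = 0.9 | Power, any product (L = 1.0) | Power, product vs none |
|---|---|---|---|---|
| 0% | 0.595/0.85 = 0.70 | 0.70 | 0.80 | 0.80 |
| 10% | 0.695/0.95 = 0.73 | 0.685/0.95 = 0.72 | 0.71 | 0.78 |
| 30% | 0.895/1.15 = 0.78 | 0.865/1.15 = 0.75 | 0.53 | 0.74 |
| 50% | 1.095/1.35 = 0.81 | 1.045/1.35 = 0.77 | 0.38 | 0.68 |
| 70% | 1.295/1.55 = 0.84 | 1.225/1.55 = 0.79 | 0.26 | 0.60 |

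The last column splits infants into lipid-rich product, other product and none; the product versus none RR is then 0.70 in every row. With L = 0.70 the any-product RR is also 0.70 in every row, so there is no dilution. At c = 70%, lotion users make up 0.70/1.55 = 45% of all users. With a = 0.60 and L = 1.0, the RR is (0.42 + c)/(0.60 + c), which gives 0.775 at c = 20% and 0.862 at c = 70%.

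**Mean-frequency variable.** If every user reports 7 days and every non-user 0, the log-RR slope per day is ln(RR)/7. That is ln(0.70)/7 = −0.0510 undiluted and ln(0.8355)/7 = −0.0257 at c = 70% with L = 1.0, about half. The documents give no distribution of days, so this shows the mechanism only.

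**Causal-pathway model, L = 1.0.** Intervention risk is 0.85 × 16.8% + 0.15 × 24% = 17.88%. Against 24% in controls the arm RR is 0.745. Within the stratum classed as users the arm RR is 16.8/24 = 0.70; within non-users it is 24/24 = 1.00. Holding any-product use fixed therefore leaves an arm effect among users, although in this set-up all of the effect comes from the product. With product use as the exposure, infants not using it have 24% risk in both arms and no arm effect remains.

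**The case against.** Four points on the other side carry weight.

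- **Product use by arm is already to be reported.** A reader might infer that the plan hides whether the arms differed in lipid-rich use. It does not: Table 4 summarises product type and named products by treatment assignment. Extra refill requests are also recorded as an adherence signal (protocol 5.2, 5.7), and SAP 5.10 raises accounting for the amount of emollient requested. The gap is confined to the 5.7 models.
- **The survey wording is not shown.** A reader might take it as settled that daily lotion will be coded as full exposure. The documents do not establish that. Table 4 lists moisturiser use separately from emollient days per week, the protocol's quarterly contacts mention only average emollient usage, and the categories for product type are not given. What stands is that no rule excludes lotion.
- **Any-emollient frequency is legitimate.** Controls are told to avoid routine emollient use of any kind unless dry skin develops, so it is the right measure of control adherence. SAP 5.7 also states a hypothesis about frequency. This stands; it is a reason to keep the variable, not to use it alone.
- **The upper figures are unfavourable cases.** The 70% is use before the trial, while controls are told to refrain and are reminded quarterly. Protocol 5.1 says most oil-in-water emollients improve the barrier, so an inert lotion is an extreme. The 85.2% comes from high-risk infants at 6 months under a different threshold. This stands, and it is why a range is shown.

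**Conclusion.** The concern holds for the SAP 5.7 association and causal-pathway models, and for the exposure definitions in 3.4 and 3.6 that feed them. They treat as equal two kinds of product that the protocol hypothesises to differ. On the stated assumptions, an RR of 0.70 would appear as 0.73 to 0.84 with 10% to 70% control use of an inert lotion, and as about 0.79 at 70% if the lotion RR is 0.9. There is no dilution if lotion is equally effective. These are illustrations: actual control lotion use, the effect of lotion and confounding by reason for use are all unknown.

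A reader might infer that the primary result is compromised. It is not: that analysis follows assigned arm, and its sample size and error rate are untouched. What is affected is the supportive analysis meant to explain that result.

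**What to change.** Before unblinding:

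1. Confirm from the survey forms that the product-type and named-product responses separate lotion from cream or ointment, in both arms and at each quarterly contact.
2. If they do, add to the SAP 5.7 models an exposure defined as days per week of a lipid-rich product (approved-list emollient, or another cream or ointment), with days of other products as a separate term. Base the association and causal-pathway interpretation on it.
3. In SAP 3.4, report intervention adherence on the lipid-rich definition. Keep any-emollient frequency as the measure of control adherence and as a parallel or sensitivity version of the association, and align 3.6.
4. If the responses do not separate the products, state that limit beside the 5.7 results.

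The cost is SAP wording and a small set of derived variables, with no new data collection if the categories suffice. The drawback is some misclassification where parents misname the product type. Harmonising the differing use thresholds (any use, more than weekly, three or more days a week) is a separate task and would not cure this.

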10.3 Power and sample size calculations

10.3.1 Power and sample size

10.3.2 Primary Outcome

For the purpose of the primary analysis, we will include a sufficient number of babies in a 1:1 ratio for the two study arms to provide an overall type I error rate of 0.05 and 80% power to detect a 30% relative reduction in cumulative incidence over 2 years (also known as

incidence proportion) of AD (RR=0.7). From our planning grant, we estimated the baseline cumulative incidence of AD in this age group and target clinics at 24% at age 2. The trials in high-risk populations of daily vs no emollient have shown reductions of 50%, we assumed a more conservative 30% reduction to 16.8%. Using the O'Brien-Fleming group sequential spending function approach, a total of 982 infants (491 per arm) are required to detect this difference in proportions. Allowing for an approximate 20% loss to follow-up, we plan to enroll **1,250** dyads (625 per arm). Sample size calculations were performed using Stat/IC version 16.1.

Table 6. Power to detect plausible interactions in exploratory analyses (Aim 2).

| Risk factor | AD risk | Prev-alence | Tx effect if RF+ | Tx effect if RF- | Tx effect DIFF | Power at $\alpha = 0.1$ |
|--------------------|---------|-------------|------------------|------------------|----------------|-------------------------|
| Family hx of atopy | 2.0 | 0.50 | 0.63 | 0.83 | -0.20 | 0.48 |
| | | | 0.60 | 0.90 | -0.30 | 0.56 |
| | | | 0.57 | 0.97 | -0.40 | 0.64 |
| High humidity | 0.8 | 0.44 | 0.82 | 0.62 | 0.20 | 0.40 |
| | | | 0.89 | 0.58 | 0.30 | 0.52 |
| | | | 0.95 | 0.54 | 0.40 | 0.65 |
| Cat owner | 1.0 | 0.30 | 0.84 | 0.64 | 0.20 | 0.36 |
| | | | 0.91 | 0.61 | 0.30 | 0.48 |
| | | | 0.98 | 0.58 | 0.40 | 0.60 |
| Dog owner | 0.7 | 0.37 | 0.84 | 0.64 | 0.20 | 0.36 |
| | | | 0.91 | 0.61 | 0.30 | 0.46 |
| | | | 0.98 | 0.58 | 0.40 | 0.59 |

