4.3. Withdrawal and Follow-Up

This study has nine participant contacts, of which three (baseline, 12 months, and 24 months) are long-form questionnaires and six (at 3, 6, 9, 15, 18, and 21 months) are short responses. At each time point, we will tabulate three categories:

- Responses, including partial responses
- Missed contacts, meaning that a later response exists
- Withdrawals and losses to follow-up, where participants either inform the research team that they will not participate further, are considered lost to follow-up meaning there is no documentation in the electronic medical record and they have no 2-year visit data available given appropriate time windows, or cannot be contacted and no later contacts exist

When participants withdraw, they may give permission to include them in the final chart review to ascertain AD diagnoses. These participants would lack follow-up survey data but be included in the final analysis of provider-diagnosed AD. The general CONSORT diagram to be populated with screening and inclusion numbers for the ITT population in the final analysis is included as Figure 2.

Within each arm, we will calculate the percentage of randomized participants at each step for each of those categories. An outline of this tabulation is provided as Figure 3.

As described in our approach to missing data in the primary analysis, we will compare loss to follow up in the intervention versus control arms with an indicator of missingness at each time point. We will test for a study arm x time interaction in a population-averaged model with missingness as a binary dependent variable. These findings will inform our approach to imputing missing observations, including outcomes.

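### Carrying the last report forward flattens any change in emollient use among non-responders, in both arms, in the quarterly adherence summaries

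*SAP*

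**What the plan says.** SAP 3.4 (Adherence) defers the method: "Frequency of emollient use will be analysed as described in section 5 below". In SAP 5.7, parent-reported days per week of use "will be summarized for the intervention and control arms for each quarterly follow-up time point from age 3 to 24 months (8 quarters"). Two rules shape those summaries. First, "we will exclude observations after a diagnosis of AD, because emollient use is likely to reflect treatment rather than prevention". Second, the rule for gaps: "For missing responses, we will carry the last observation forward. Distributions over time will be graphed". No other method for missing use reports is stated.

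SAP 4.3 expects two kinds of gap. Permanent withdrawal or loss is one. The other is "Missed contacts, meaning that a later response exists". Both are to be tabulated by arm at each contact (SAP Figure 3), and for missingness itself: "We will test for a study arm x time interaction in a population-averaged model with missingness as a binary dependent variable". SAP 4.3 says the findings will inform imputation. It does not say that they would change the carry-forward rule in 5.7.

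**The concern.** Parent surveys are the main measure of adherence. Used containers are not collected (Protocol 5.6), and the only other indicator named is requests for extra refills (Protocol 5.7). Control families can buy emollient freely. How far the arms separate in use therefore bears on how a null or weak result is read: either emollient does not prevent AD, or it was not used differently enough to tell.

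Carrying forward records zero change for everyone who has stopped answering. The quarters with the fewest answers are then the ones shaped most by old answers. Intervention use that wanes unseen stays on the graph at its earlier level. A control parent who later starts regular use stays at the earlier low level. In both cases the arms look better separated late in follow-up than they are.

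There is some documentary reason to think that non-use and withdrawal go together. A working note in SAP 5.12 says that families seeking partial withdrawal often make contact soon after randomization because they cannot fully comply, though some may still complete questionnaires.

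**Working it through.** The plan gives no expected use level and no survey response rate, so there is no figure of its own to reproduce. All use and response values below are assumptions.

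**1. Bias at a given quarter.** Bias = m × (mean last report of non-responders − their mean current use), where m is the share of values carried. It is zero if use is stable.

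**2. Permanent non-response unrelated to use.** Let use change evenly by D over the 7 steps between 8 quarters, and let non-response build up evenly. Last reports are then spread evenly over quarters 1 to 7, on average 4 steps before the end. The bias at 24 months is m × D × 4/7, and the share of the true change still visible is 1 − 4m/7. For use falling from 6 to 4 days per week (D = 2):

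| Not responding at 24 months | Bias (days/week) | Value shown (true 4.0) | Change still visible |
|---|---|---|---|
| 10% | 0.11 | 4.11 | 94% |
| 20% | 0.23 | 4.23 | 89% |
| 30% | 0.34 | 4.34 | 83% |
| 40% | 0.46 | 4.46 | 77% |
| 50% | 0.57 | 4.57 | 71% |

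**3. Control arm, 20% not responding.** If use rises from 2 to 4, the curve shows 4 − 0.23 = 3.77, which understates use. If use falls from 3 to 1, it shows 1 + 0.23 = 1.23, which overstates use. Controls are asked not to use emollient (SAP 3.4: "while those in the control arm are asked to refrain from emollient use"), so the first case flatters control adherence and the second does the reverse.

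**4. Proportion of regular users.** Assume use falls from 85% to 50% and response from 95% to 70%, unrelated to use.
- Permanent non-response: of those who ever answered, m = 1 − 70/95 = 0.263. Bias = 0.263 × 35 × 4/7 = 5.3 points, so the curve shows about 55%.
- Intermittent gaps, independent between quarters: 0.70 × 50 + 0.30 × 0.736 × 55 + 0.30 × 0.264 × 0.771 × 60 + smaller terms = 35.0 + 12.1 + 3.7 + 1.2 = 52%.
- Observed values only: 50%, which is correct in this setting.

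**5. When non-users answer less often.** Keep the same use and overall response, but let non-users answer 0.6 times as often, with intermittent gaps. Observed values give 50/(50 + 0.6 × 50) = 62.5%. Carrying forward gives 54% (simulated). The true value is 50%, so observed-only is further off.

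A simulation in days per week, with 40% permanently lost and low users leaving first, shows the same ordering: true 3.98, carried forward 4.43, observed-only 4.64. If those who leave also stop use entirely, the truth drops to 2.78 and the other two figures do not move.

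**6. Using earlier reports in estimation.** In the declining scenarios simulated, estimates that used earlier reports were closer to the truth than carrying forward (50% to 54% where the truth was 50%). With flat use they agreed with it.

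**The case against.** The strongest case against has four parts.

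- **Direction.** A reader might infer that late adherence is overstated by construction. The documents do not support that. Neither says that use is expected to fall, and in the control arm the sign can go either way. Only the flattening is built in.
- **Amount missing.** A reader might take the sample-size allowance ("Allowing for an approximate 20% loss to follow-up, we plan to enroll") as the survey loss. It is not: Protocol 4.7.3 defines loss to follow-up from the health record. Response need not fall steadily either. Protocol Table 2 pays for the enrollment, 12-month and 24-month questionnaires, and the 12- and 24-month contacts have wide windows (SAP Table 2). The 24-month point may be better covered than the unpaid quarters.
- **Remedy.** A reader might infer that carrying forward is always worse than showing observed answers. Step 5 shows the opposite can happen.
- **Importance.** The quarterly summaries are descriptive, and the planned between-arm comparison of use rests on each child's average. Figure 3 will show how much is missing. SAP Table 4 lists quarterly use by assignment without saying whether values are carried. SAP 5.10 suggests that emollient requests may be looked at. Protocol 5.7 says a pragmatic design puts less weight on adherence monitoring.

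The first three parts stand and limit the claim. The fourth stands as to rank, but it does not dispose of the point. Knowing how many answers are missing does not correct the curve, Table 4 is silent on the method, and no planned analysis tests the carry-forward rule. Protocol 13.3 commits the trial to multiple imputation and sensitivity analyses for missing data; these summaries receive neither.

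**Conclusion.** The concern holds in a limited form. As written, SAP 5.7 flattens any change in emollient use that occurs after a parent's last answer, in either arm. It overstates late intervention-arm use only if non-responders reduce use. In the illustrations where non-response is unrelated to use, the error at 24 months is 2 to 5 percentage points for a fall from 85% to 50%, or 0.11 to 0.57 days per week for a two-day fall. It is larger if families stop answering and stop use together. These sizes rest entirely on assumed response and use patterns.

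The primary intention-to-treat analysis is not affected. The point is confined to the by-arm quarterly adherence summaries, and it is worth acting on because they inform how a null or weak result is read.

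**What to change.** Amend SAP 5.7 before the data are locked:

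1. Replace carrying forward, as the main method for the quarterly summaries, with arm-by-quarter estimates from a mixed model with arm, quarter and arm × quarter, or with multiple imputation using earlier and later reports. Keep the exclusion of quarters after an AD diagnosis and say that those quarters are not imputed.
2. Show observed values with the number responding in each arm and quarter alongside. Do not make them the sole replacement, because they can be more biased than carrying forward when non-users stop answering.
3. Add one sensitivity analysis that counts intervention-arm non-responders as non-users. A model that relies on earlier reports cannot see use that stops when answers stop.
4. State which method Table 4 uses, and whether carried values enter each child's average.

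The cost is SAP wording and a little more analysis, on data already being collected. Late adherence may look less favourable than under the current rule.
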